1 DEFINITIONS

Term	Definition
Adverse Event (AE)	Any untoward medical occurrence, unintended disease or injury, untoward clinical signs (including abnormal laboratory findings) in subjects, users or other person, whether or not related to the medical device.
Engel Classification	 Class I: Free of disabling seizures IA: Completely seizure-free since surgery IB: Non disabling simple partial seizures only since surgery IC: Some disabling seizures after surgery, but free of disabling seizures for at least 2 years ID: Generalized convulsions with antiepileptic drug withdrawal only Class II: Rare disabling seizures ("almost seizure-free") IIA: Initially free of disabling seizures but has rare seizures now IIB: Rare disabling seizures since surgery IIC: More than rare disabling seizures after surgery, but rare seizures for at least 2 years IID: Nocturnal seizures only Class III: Worthwhile seizure reduction IIIA: Worthwhile seizure-free intervals amounting to greater than half the follow-up period, but not less than 2 years Class IV: No worthwhile improvement IVA: Significant seizure reduction IVB: No appreciable change IVC: Seizures worse
ILAE (International League Against Epilepsy) Classification	 Class 1: Completely seizure free; no auras Class 2: Only auras; no other seizures Class 3: 1 to 3 seizure days per year; ± auras Class 4: 4 seizure days per year to 50% reduction of baseline seizure days; ± auras Class 5: Less than 50% reduction of baseline seizure days; ± auras Class 6: More than 100% increase of baseline seizure days; ± auras
Index Procedure	First NeuroBlate [®] System procedure after signing the LAANTERN Informed Consent Form.

Term	Definition
Karnofsky Performance Scale (KPS)	 The KPS will be collected for brain malignancy subjects only, and for subjects 16 years and older. The scale runs from 100 to 0, where 100 is "perfect" health and 0 is death: 100 - Normal; no complaints; no evidence of disease. 90 - Able to carry on normal activity; minor signs or symptoms of disease. 80 - Normal activity with effort; some signs or symptoms of disease. 70 - Cares for self; unable to carry on normal activity or to do active work. 60 - Requires occasional assistance but is able to care for most of his personal needs. 50 - Requires considerable assistance and frequent medical care. 40 - Disabled; requires special care and assistance. 30 - Severely disabled; hospital admission is indicated although death not imminent. 20 - Very sick; hospital admission necessary; active supportive treatment necessary. 10 - Moribund; fatal processes progressing rapidly. 0 - Dead
Lansky Performance Scale (LPS)	The LPS will be collected for brain malignancy subjects only, and for subjects between 1 year and 16 years of age. The scale runs from 100 to 0, where 100 is "perfect" health and 0 is death: 100 – Fully active, normal 90 – Minor restrictions in strenuous physical activity 80 – Active, but gets tired more quickly 70 – Greater restriction of play and less time spent in play activity 60 – up and around, but active play minimal; keeps busy by being involved in quieter activities 50 – Lying around much of the day, but gets dressed; no active playing participates in all quiet play and activities 40 – Mainly in bed; participates in quiet activities 30 – Bedbound; needing assistance even for quiet play 20 – Sleeping often; play entirely limited to very passive activities 10 – Doesn't play; does not get out of bed 0 – Unresponsive
Serious Adverse Event (SAE)	 Adverse Event that: (a) Led to death (b) Led to serious deterioration in the health of the subject, that either resulted in life-threatening illness or injury A permanent impairment of a body structure or a body function In-patient or prolongation of existing hospitalization Medical or surgical intervention to prevent permanent impairment to a body structure or a body function (c) Led to fetal distress, fetal death or a congenital abnormality or birth defect

2 ABBREVIATIONS

Abbreviation	Term				
AE	Adverse Event				
CNS	Central Nervous System				
eCRF	electronic Case Report Form				
EDC	Electronic Data Capture				
EQ-5D or EQ-5D -Y	EuroQol-5 Dimensions adult or youth version				
FACT-Br or FACT-Peds-Br	Functional Assessment of Cancer Therapy-Brain adult or pediatric version				
FDA	Food and Drug Administration				
ICF	Informed Consent Form				
ID	Identification Number				
IFU	Instructions For Use				
ILAE	International League Against Epilepsy				
IRB	Institutional Review Board				
KPS	Karnofsky Performance Scale				
LITT	Laser Interstitial Thermal Therapy				
LPS	Lansky Performance Scale				
MRI	Magnetic Resonance Imaging				
NBS	The NeuroBlate [®] System				
OS	Overall Survival				
PFS	Progression Free Survival				
PI	Primary Investigator				
QOL	Quality of Life				
QOLIE-31 or QOLIE-48	Quality of Life in Epilepsy Inventory adult or pediatric version				
SAE	Serious Adverse Event				
VAS	Visual Analog Scale				

3 BACKGROUND & PURPOSE

Laser interstitial thermal therapy (LITT) is a minimally invasive technique to necrotize intracranial abnormal tissues, originally introduced in 1983. Its use in neurosurgical procedures was historically limited by early technical difficulties related to the monitoring and control of the extent of thermal distribution. The development of magnetic resonance thermography and its application to LITT has allowed for real-time thermal imaging and feedback control during laser energy delivery, allowing for precise and accurate delivery of tissue hyperthermia. Improvements in laser probe design, surgical stereotactic targeting hardware, and computer monitoring software has accelerated acceptance and clinical utilization of LITT as a neurosurgical treatment alternative. There is limited outcome data available from utilization of current commercially available LITT systems.

The NeuroBlate[®] System (NBS) is a minimally invasive robotic laser thermotherapy tool that is manufactured by Monteris Medical. It employs a pulsed surgical laser to deliver targeted energy to abnormal brain tissue. With the NBS, a surgeon makes a small hole in the skull, approximately as wide as a pencil. A small probe is then used to deliver laser light energy to heat and destroy the target tissue. The NBS combines magnetic resonance imaging (MRI) and software-based visualization to necrotize targeted tissues in locations in the brain, either superficial or deep. During the procedure, a surgeon operates the ablation remotely through a computer module. An MRI-compatible robotic probe driver helps the surgeon precisely guide the laser probe to the planned ablation area and apply heat in controlled amounts, until the targeted tissue is destroyed.

To further understand performance and utilization of the NBS in current standard of care, a post-market multi-center registry, LAANTERN (Laser Ablation of Abnormal Neurological Tissue using Robotic NeuroBlate[®] system), is designed to collect baseline, procedural and follow-up data on subjects that are to undergo thermal therapy using the NBS. The LAANTERN registry is conducted in an observational manner with objectives designed for publication purposes.

4 STUDY DEVICE

Any commercially available component of NeuroBlate[®] System may be used for the registry which includes, probe, robotic probe driver, and software. For more details regarding system description and principle of operation, please refer to the most current Instructions for Use (IFU) found at https://www.monteris.com/ifu/

5 STUDY DESIGN OVERVIEW

This is a prospective multi-center registry that will include data collection at baseline (prior to NBS procedure, which is also referred as the index procedure), index procedure, discharge and up to 5 years of follow-up including data from additional NBS procedures. Up to 3,000 subjects may be enrolled at up to 50 study sites. Some subjects may be enrolled in sub-studies associated with LAANTERN as per site participation and sub-study specific consent.

5.1 STUDY OBJECTIVES

Objective 1: Safety

Observe safety profile described by NBS or surgical-related SAEs

Objective 2: Reason for NeuroBlate®

Objective 3: Procedural Outcomes

- Local Control
- Progression Free Survival
- Overall Survival
 - Seizure Freedom
 - Engel and ILAE Classification

Objective 4: Cognitive & Quality of Life Outcomes

Collected for subjects based on their disease etiology and age.

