8.1 REPORTING OF ADVERSE EVENTS BY CLINICAL SITES

The following adverse events (AE) are considered reportable for this study, as determined by PI discretion:

NeuroBlate[®] System related AEs

• Adverse events related to the NeuroBlate® System Device (i.e. probe, robotic probe driver, software)

NeuroBlate[®] Procedure related AEs

 Adverse events that occur due to a NeuroBlate[®] (LITT) procedure and cannot be directly attributed to the NBS Device or surgical procedure

Surgical Procedure related AEs

• Adverse events that occur due to the surgical procedure and cannot be directly attributed to NeuroBlate[®] System or procedure (i.e. biopsy related event)

The following adverse events are considered not reportable for this registry:

- Planned hospitalization for a pre-existing condition without serious deterioration in health.
- Any expected postoperative complaints or symptoms such as pain at biopsy site, headaches, weakness, cerebral edema, and transient events (less than 30 days from procedure) that do not require intervention. If the event involves a clinically significant change in severity or duration of symptoms or requires clinical intervention that is different from ordinary postoperative care, the event is considered a reportable AE.

Reportable AEs must be described by duration (start and resolution dates), relationship to the NeuroBlate[®] System or surgical procedure, action taken to resolve the event, and outcome of the event. Additional information, such as procedural notes, treatment notes, or clinical summary may be requested as supporting documentation.

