8.2 ADVERSE EVENT RELATEDNESS

The relationship of the AE to the NeuroBlate[®] System Device (NBS) or the NeuroBlate[®] (LITT) procedure or surgical procedure will be determined by the Primary Investigator (PI) based upon the following definitions.

Definite: The AE follows a reasonable temporal and causative sequence from receipt (or attempted receipt) of the device treatment or procedure.

Possible: The AE follows a reasonable temporal sequence from receipt of the device treatment or procedure and the possibility of device treatment or procedure involvement cannot be excluded. However, other factors such as underlying disease, concomitant medications, or concurrent treatment are presumable.

Not Related: The AE has no temporal sequence from receipt of the device treatment or procedure, or it can be explained by other factors, including underlying disease, concomitant medication, or concurrent treatment. Note: If the event is determined to be "Not Related" to either the NBS or the Surgical Procedure, it is not considered a reportable AE.

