8.3 SAFETY COMMITTEE

A Safety Committee will be used to review reported events to provide unbiased third-party adjudication for publications.

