15 INVESTIGATOR REPORTS AND RECORDS REQUIREMENTS

The Investigator is responsible for the completion and submission to the Sponsor of all CRFs, AEs or other reportable study events (e.g. procedure related complications), and deviations from the protocol. If any action is taken by an IRB with respect to the study, the information must be forwarded to the Sponsor in a timely manner.

The Investigator shall prepare and submit complete, accurate, and in a timely manner, the reports listed in Table 2 below. In addition to this list, individual IRBs may add additional requirements and/or require a different notification time frame.

. -

-

Type of Report	Notification prepared by Investigator for	Notification Time Frame		
Reportable Serious Adverse Events as Described in Section 8	Sponsor	As soon as possible, preferably		
Death or Serious Adverse Event	IRB per policy	within 48 hours after discovery of event.		
Withdrawal of IRB Approval	Sponsor	Within five (5) working days.		
Deviations to the Protocol	Sponsor IRB per policy	As soon as possible after occurrence of deviation.		

All data must be stored and retained by the investigative site for a minimum of 2 years following a notification from Sponsor that all investigative sites are complete, terminated, or discontinued. Should the investigator withdraw from the responsibility of retaining study records, then custody of the records transfers to a person assuming responsibility. Sponsor will be notified in writing of new custodian by the investigative site.

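### Objective 1 and the section 8.2 Note name two relatedness classes where section 8.1 defines three, so the text conflicts on whether SAEs due only to the LITT procedure are reportable and counted

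*Protocol*

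**What the plan says.** Objective 1 in protocol section 5.1 reads "Observe safety profile described by NBS or surgical-related SAEs".

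Section 8.1 makes three classes of event reportable, at the investigator's discretion:

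- Events related to the device, given as "System Device (i.e. probe, robotic probe driver, software".
- Events due to the NeuroBlate (LITT) "procedure and cannot be directly attributed to the NBS Device or surgical procedure".
- Events due to the surgical procedure, for example a biopsy, that are not directly attributable to the NeuroBlate System or procedure.

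The last paragraph of 8.1 says what must be recorded for each event. It asks for the relationship to the NeuroBlate "System or surgical procedure, action taken to resolve the event, and outcome of the event".

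Section 8.2 opens by having the investigator judge the relationship to the "System Device (NBS) or the NeuroBlate" (LITT) procedure or the surgical procedure. It closes with a Note: if an event is judged 'Not Related' "to either the NBS or the Surgical Procedure, it is not considered a reportable AE".

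The SAP defines neither a safety outcome nor a relatedness class. Section 10 of the protocol promises descriptive summaries only.

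**The concern.** The LITT class holds events due to the ablation procedure that are put down neither to a device component nor to the surgery. In a registry of laser ablation this can include harm from the ablation itself when the device worked as intended, which is close to the centre of what Objective 1 should describe. Yet the sentence that sets the outcome and the sentence that switches reporting off both omit this class.

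The later steps would not reliably recover an event left out this way. The sponsor-notification row of Table 2 in section 15 covers "Reportable Serious Adverse Events as Described in Section 8", so it inherits whatever section 8 is taken to mean. Section 8.3 says "A Safety Committee will be used to review reported events", so adjudication starts from what sites have sent. A descriptive summary cannot count an event that is not in the data. With up to 50 sites, some could work from the 8.1 list and others from the Note, and their SAE rates would then differ because of wording.

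**Working it through.** No arithmetic applies. The plan states no SAE rate, no hypothesis and no derived sample size, so there is no figure to reproduce. The check sets the relatedness statements side by side and then follows one event through them.

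**Step 1. Classes named in each place**

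| Place in protocol | Device / NBS / System | LITT procedure | Surgical procedure | Classes |
|---|---|---|---|---|
| 5.1, Objective 1 | yes | no | yes | 2 |
| 8.1, list of reportable events | yes | yes | yes | 3 |
| 8.1, what to record | yes | no | yes | 2 |
| 8.2, opening sentence | yes | yes | yes | 3 |
| 8.2, Note | yes | no | yes | 2 |

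Three statements name two classes and two name three. The class missing is the LITT procedure each time.

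**Step 2. What NBS means**

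- Section 2 expands NBS as the NeuroBlate System.
- Section 3 describes it as a tool.
- Section 4 gives its components as probe, robotic probe driver and software, the same three that define the device class in 8.1.
- The opening of 8.2 attaches the label NBS to the device and names the LITT procedure as a separate item. The Note stands in that same section, so the device is the most natural meaning there.
- In the other direction, section 5 uses NBS as the name of the index procedure, and the SAP does the same in its paragraph on censoring and truncation.

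**Step 3. One event followed through the text**

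Take an SAE judged Definite for the LITT procedure and Not Related to the device and to the surgery. I read the Note's 'either' as meaning unrelated to both.

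- Under the 8.1 list it is reportable.
- Under the 8.2 Note, with NBS as the device, it is not reportable.
- Under Objective 1, with NBS as the device, it is outside the safety profile even if it is reported.
- With NBS read to include the NBS procedure, it is reportable and counted throughout.

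The result depends on which sentence governs and on what NBS covers. The protocol settles neither.

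**Step 4. Two separate effects**

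The Note acts on reporting, site by site. Objective 1 acts on the definition of the outcome, for every site at once. Correcting one leaves the other in place, so both need the edit.

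**The case against.** The strongest reply is that the protocol plainly intends to capture these events. Five points support it.

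- Section 8.1 lists LITT-procedure events as reportable in so many words, and the opening of 8.2 tells the investigator to judge that relationship. To lose an event, an investigator would have to let a closing note override both.
- The grades in 8.2 are defined against receipt of the device's treatment or the procedure. Ablation harm follows that treatment in time, so it would often be graded at least Possible. An event that cannot be attributed directly to the device is not thereby unrelated to it.
- The opening paragraph of section 15 gives procedure-related complications as an example of a reportable event, and the Table 2 row points to section 8 as a whole, which includes the three-class list.
- Section 7.3 says that adverse events associated with additional NeuroBlate procedures are collected, although its last sentence returns to reportable events.
- NBS is used for the treatment as well as the equipment, and Objective 1 is a one-line summary.

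Most of this stands. It makes inclusion the likely intention and non-reporting less likely than the Note alone would suggest. It does not remove the Note, which is an explicit rule that conflicts with 8.1 on its literal terms, and it leaves the outcome in Objective 1 open to two meanings.

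A reader might go further and infer that LITT-related SAEs have gone missing, or that the registry's SAE rate is understated by some fraction. The documents do not support that. They show no lost event and give no event rates, no split by class and no information on how sites read the Note. The eCRF, which would show which relationships are captured, is not among them. Any percentage would rest on invented inputs. For the same reason, a retrospective query to all sites is not justified on this evidence.

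**Conclusion.** The inconsistency is real and is in the current protocol. Three statements omit a class that two others include, and one of the three is a rule that removes events from reporting. The adverse consequence depends on two conditions: that NBS is read as the device, as 8.2 labels it, and that an investigator grades a LITT-only event as unrelated to both device and surgery. If both are met, the event is non-reportable under the Note. If NBS in Objective 1 is read the same way, a LITT-only SAE also falls outside the safety profile, whether or not it was reported.

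Loss is possible but not shown, and its size cannot be estimated from the documents. If all sites and the analysis already use the broad reading, nothing has been lost and the edits change no data. The case for acting is that the ambiguity touches the registry's first objective and costs little to remove.

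**What to change.** Make three edits so that every statement names the same classes:

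1. **Objective 1:** describe the safety profile by SAEs related to the NBS device, the NeuroBlate (LITT) procedure or the surgical procedure, reported in total and by class.
2. **Section 8.2 Note:** an event is not reportable only if it is judged 'Not Related' to all three.
3. **Section 8.1, what to record:** record the relationship to each of the three.

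The cost is a protocol wording amendment and a memo to sites. The reported SAE rate may rise slightly if some sites had been following the Note. In that case, publications spanning the change should state which definition applied.

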5.2 STUDY POPULATION

Subjects who meet inclusion criteria and no exclusion criteria and sign the Informed Consent Form (ICF) (CL10030) will be considered enrolled in this study. At the time of enrollment, a unique identification number (ID) will be assigned to the subject and used to collect all study information via electronic Case Report Forms (eCRFs).

Inclusion Criteria:

- 1. Subject or legally authorized representative provides written authorization and/or consent
- 2. Subject who is to undergo thermal therapy by the NeuroBlate[®] System for treatment of their neurological disorder

Exclusion Criteria:

- 1. Subject who is, or is expected to be inaccessible for follow-up
- 2. Other concurrent medical or other condition (chronic or acute in nature) that, in the opinion of the investigator, may prevent participation or otherwise render patient ineligible for the study

6 INFORMED CONSENT (ICF)

The Sponsor will provide a template ICF to each site for IRB submission prior to the site initiation. This template may be modified to suit the requirements of the individual study site. The Sponsor must preapprove all changes to the ICF prior to initial submission to the IRB. A copy of the IRB-approved ICF must be sent to the Sponsor and the original copy must be retained at the study site. If the ICF is amended by the reviewing IRB, the Sponsor must pre-approve all changes to the ICF prior to submission. In addition, a copy of the approved documents must be provided by the Investigator to the Sponsor prior to enrollment of subjects in the study.

The Investigator or assigned designee must administer this approved ICF to each prospective study subject and obtain the subject's signature or a legally authorized representative signature along with the date of consent prior to enrollment in the study. The ICF must be obtained in accordance with 21 CFR Part 50. Subjects must be informed about their right to withdraw from the study at any time and for any reason without sanction, penalty, or loss of benefits to which the subject is otherwise entitled and informed that withdrawal from the study will not jeopardize their future medical care. A copy of ICF must be given to each subject enrolled in the study. The institutional standard subject consent form does not replace the study ICF.

[figure not shown]
7 STUDY VISITS

A subject follow-up schedule is intended to align with typical standard of care practices. Data may be collected during in-office subject visits or remotely (e.g. telephone, email, or mail), when feasible and appropriate. These modes of data collection aim to help facilitate robust and reliable long-term surveillance and survival data collection. For this standard of care registry, the visit windows are continuous, however target visit dates are provided below. Visits should be completed near the target visit date or be the most complete visit within the visit window. A visit window tool is available in the EDC system. Figure 1 indicates the sequence of subject visits.

Target Visit Dates:

- Baseline within 60 days prior to the Index Procedure
- Index Procedure Day 0
- Discharge N/A
- 1 Month Follow-up Visit Day 30
- 3 Month Follow-up Visit Day 90
- 6 Month Follow-up Visit Day 180
- 1 Year Follow-up Visit Day 365
- 2 Year Follow-up Visit Day 730
- 3 Year Follow-up Visit Day 1095

- 4 Year Follow-up Visit Day 1460
 5 Year Follow-up Visit Day 1825

